14.2.1 Power and sample size determination

Power for the Wilcoxon signed-rank test is calculated by simulation using a truncated log-normal distribution parameterized according to Kabasakal et al.¹⁵ (median = 5, range = 1 to 25) to sample the total number of lesions in patients

across a range of samples. With a total of $N = 48$ patients assessed by both modalities, there will be 80% power to conclude non-inferiority equivalence if the two methods are equivalent ($\Delta = 0$).

The distributions of number of lesions detected by $[^{18}\text{F}]\text{-FET-}\beta\text{AG-TOCA}$ – PET/CT and by $[^{68}\text{Ga}]\text{-DOTA-peptide-PET/CT}$ will be summarized, and will be compared using the Wilcoxon signed-rank test with the pre-specified level of equivalence of $\Delta = 0.64$ and a one-sided alpha= 0.1.

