6.2 Secondary objectives

To assess efficacy of [^{18}F]-FET- β AG-TOCA PET/CT in patients with a histological diagnosis of NET and with measurable disease, who have and have not had [^{68}Ga]- DOTA-peptide imaging

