7.2.2 Secondary

2. Compare diagnostic efficacy of [¹⁸F]-FET-βAG-TOCA in those patients who have had or not had or are due to have [⁶⁸Ga]-DOTA-peptide imaging. A power of $\geq 80\%$ has been chosen to conclude non-inferiority equivalence.

*Note** (All patients with a histological diagnosis of NET and lesion on CT is $\geq 1\text{cm}$ irrespective of whether they have had a [⁶⁸Ga]-DOTA-peptide scan or are waiting for one as part of their management will be included in study).*

3. Comparison of [¹⁸F]-FET-βAG-TOCA PET/CT scan and central review (nuclear medicine and radiology physician experts) of all imaging received by patient. (To account for any discrepancy that may exist between CT, [⁶⁸Ga]-DOTA-peptide imaging and [¹⁸F]-FET-βAG-TOCA PET/CT scan, then patients will be offered an MRI scan.

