8. STUDY OUTLINE

8.1 Study design and rational of the chosen approaches

The total sample size will be 56 patients. Patients from cohort 1 (n=8-12), 4-6 female and 4-6 male (each cohort minimum 3) will be used in the final analysis. Patients with locally advanced or metastatic NETs of any site will be recruited from the Endocrinology, Surgical and Oncology Outpatients clinic, Hammersmith and Royal Free Hospitals. After obtaining informed consent, eligible patients will have blood taken at baseline for FBC, EUC, LFTs (routine clinical practice), and serum biomarkers. Patients will undergo routine staging. In addition, patients will undergo $[^{18}\text{F}]\text{-FET-}\beta\text{AG-TOCA}$ PET/CT scanning at Imanova. Patients' original diagnostic tumour biopsy (paraffin fixed) will be obtained.

8.1.1 Cohort 1. Dosimetry and safety study in patients with histological diagnosis of NETs of any site.

In this initial evaluation patients presenting for routine staging will be consented to undergo whole body dynamic scanning (multiple whole body scans up to 3.5 hours) with metabolite analysis in order to develop a suitable protocol for static scanning that will be used for patients in cohort 2. We will also calculate the internal radiation dosimetry, which may alter the administered dose in subsequent studies. Although we do not expect any toxicity, we will conduct detailed safety assessment in this group of patients. We require a minimum of 8 patients for final Dosimetry and safety analysis, which should include a minimum of either 3 male or 3 female subjects. To ensure both sexes are sufficiently represented in the final Dosimetry, for calculating effective dose, Cohort 1 will therefore include a minimum of 8, but up to 12 subjects.

8.1.2 Cohort 2. Open label study assessing tumoural uptake of $[^{18}\text{F}]\text{-FET-}\beta\text{AG-TOCA -PET}$ in patients with histological diagnosis of NETs of any site.

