9. ELIGIBILITY

9.1 Inclusion criteria

1. Written informed consent
2. Age \geq 18 years
3. Histological diagnosis of NET of any site, except where ENETS criteria does not mandate histology for confirmation of diagnosis or patients who have a positive $^{68}\text{Gallium-peptide}$ scan in whom NET diagnosis is pre-operatively definitive.
4. Locally advanced or metastatic disease
5. Eastern Cooperative Oncology Group (ECOG) performance status of ≤ 2 (appendix A)
6. Life expectancy > 3 months
7. Measurable disease defined as a lesion that can be accurately measured in at least one dimension with the longest diameter $\geq 10\text{mm}$ using conventional techniques
8. Somatostatin receptor imaging within 6 months. (if patient does not have somatostatin receptor imaging they may also be included provided they have measurable disease ($\geq 10\text{mm}$) on conventional imaging).
9. Adequate organ system function as defined in Table 1

Table 1 clinical laboratory parameters

| System | Laboratory Values |
|-------------------------------------------------------------------|------------------------------------------------------------------------------------------|
| Hematologic | |
| Absolute neutrophil count (ANC) | $\geq 1.5 \times 10^9/\text{L}$ |
| Hemoglobin ¹ | $\geq 9 \text{ g/dL}$ (5.6 mmol/L) |
| Platelets | $\geq 100 \times 10^9/\text{L}$ |
| Prothrombin time (PT) or international normalized ratio (INR) | $\leq 1.2 \times$ upper limit of normal (ULN) |
| Partial thromboplastin time (PTT) | $\leq 1.2 \times$ ULN |
| Hepatic² | |
| Total bilirubin | $\leq 1.5 \times$ ULN |
| AST and ALT | $\leq 2.5 \times$ ULN |
| Renal | |
| Serum creatinine | $\leq 1.5 \text{ mg/dL}$ (133 $\mu\text{mol/L}$) |
| Or, if greater than 1.5 mg/dL: Calculated creatinine clearance | $\geq 50 \text{ mL/min}$ |
| 1 | Subjects may not have had a transfusion within 7 days of screening assessment. |
| 2 | Concomitant elevations in bilirubin and AST/ALT above $1.0 \times$ ULN are not permitted |

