10.2 Withdrawal criteria

Whatever the disease status, the treatment will always be discontinued in case of patient refusal.

Each patient is free to withdraw from the study at any time.

A complete final evaluation at the time of the subject's withdrawal will be made and an explanation given of why the patient is withdrawing or being withdrawn from the study.

The reason for non-completion and the date and time of the last contact with the patient must be noted in the case report form (CRF).

In the case of patients withdrawal before or after dosing (ie, non-evaluable subjects) additional patients may be enrolled to reach a total of 56 evaluable patients.

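### The 80% power for the lesion comparison needs 48 patients with both scans, which no rule secures, and the parameter behind the 0.64 margin and the number of bounds are not stated

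*Combined protocol and SAP*

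**What the plan says.** **Power basis.** Section 14.2.1 samples total lesions per patient from a truncated log-normal distribution (median 5, range 1 to 25). It states that with 48 "patients assessed by both modalities, there will be 80% power to conclude non-inferiority equivalence" if the true difference is zero. Numbers of lesions on the 18F scan and the Ga-DOTA-peptide scan are compared by the Wilcoxon signed-rank test, with an equivalence level of 0.64 and a one-sided alpha of 0.1.

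**Who may enter.**
- Section 6.2 covers patients with NET "and with measurable disease, who have and have not had" Ga-peptide imaging.
- The note in 7.2.2 says that patients with a CT lesion of at least 1 cm, whether they have already had a Ga-peptide "scan or are waiting for one as part of their management will be included in study".
- Section 9.1, criterion 8, asks for somatostatin receptor imaging within 6 months, but "if patient does not have somatostatin receptor imaging they may also be included provided they have measurable disease" of at least 10 mm.
- Section 12.1.1 lists somatostatin receptor imaging within 6 months under screening, and 13.2 calls the Ga scan an entry qualification.

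**Which scans are collected.** Section 11.1 retrieves a Ga-peptide scan if one has been performed within 6 months of the 18F scan. Item 3 of 7.2.2 adds a central review "of all imaging received by patient".

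**Numbers.** The total is 56, with 8 to 12 in cohort 1. Section 8.1 ends its sentence on cohort 1 with "each cohort minimum 3) will be used in the final analysis", while 8.1.1 says "We require a minimum of 8 patients for final Dosimetry and safety analysis". Under 10.2, after a withdrawal, "additional patients may be enrolled to reach a total of 56 evaluable patients".

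**The concern.** This is the only comparison in the plan with a stated power, and 7.2.2 repeats that power in the secondary endpoint. A signed-rank test uses only patients with both counts. If some patients never have a Ga scan, or have one that is not retrieved, the test runs on fewer pairs than its power was computed for, and nothing in the plan would trigger a correction.

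The second problem is what a positive result would mean. The plan names the variable and the test, but not the parameter that 0.64 limits (mean, pseudomedian or a ratio), nor whether one or two bounds are tested. A reader told that the new tracer met the margin could not say what loss of lesions had been excluded.

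**Working it through.** **1. Pairs available.** If only cohort 2 is compared, 56 - 12 = 44 to 56 - 8 = 48 patients are available. At 48 none can be spared, and at 44 the power basis is already missed. If cohort 1 counts, 56 - 48 = 8 may be unpaired, or 8/56 = 14%.

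The entry passages do not close the gap. The waiver in criterion 8 requires a lesion of at least 10 mm, which criterion 7 already requires of everyone, so the waiver is open to every patient. Criterion 8 and section 12.1.1 ask for somatostatin receptor imaging in general, not a Ga-peptide PET/CT. Section 10.2 is triggered by withdrawal, not by a missing second scan. Section 11.1 is worded for scans already performed; no interval or retrieval step is stated for a Ga scan done later.

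**2. The plan's 80%.** It cannot be reproduced, because 14.2.1 models total lesions only. The within-patient discordance between scans, the log-scale SD and the number of bounds are not given. In simulations with 48 pairs from the stated distribution, under assumed log-scale SDs and pairing models, one-bound power ran from about 30% (independent counts) to about 100% (shared lesions, each detected with probability 0.8 or more). Some assumed settings land within 2 points of 80%.

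**3. Effect of losing pairs.** Take the 80% as given and solve for the paired SD it implies, with 0.64 in lesions (normal approximation).

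- One bound: SD = 0.64 × √48 / (1.2816 + 0.8416) = 2.09. Power = Φ(0.64√n/SD - 1.2816).
- Two bounds: SD = 0.64 × √48 / (2 × 1.2816) = 1.73. Power = 2Φ(0.64√n/SD - 1.2816) - 1.

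| Pairs | 80% is for one bound (SD 2.09) | 80% is for two bounds (SD 1.73) |
|---|---|---|
| 48 | 80% | 80% |
| 44 | 77% | 76% |
| 36 | 71% | 65% |
| 24 | 59% | 40% |

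If the 80% is for one bound but two are tested, power at 48 pairs is 2 × 0.80 - 1 = 60%.

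**4. The margin read as lesions per patient.** The non-inferiority test ranks |d + 0.64|, where d is a whole number (18F minus Ga). For any margin between 0.5 and 1, the order of d is -1, 0, -2, +1, -3, +2 and so on. The ranks, and hence p, are therefore the same for every margin in that range. In 3,000 simulated data sets with margins from 0.501 to 0.999, the largest difference in p was 0.

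Example with 48 pairs: 38 tied and 10 patients losing 5 lesions each.
- The ties share rank 19.5, sum 38 × 19.5 = 741. The losses share rank 43.5, sum 10 × 43.5 = 435.
- z = (741 - 435) / √(38 × 19.5² + 10 × 43.5²) = 306 / 182.7 = 1.675, so p = 0.047 and non-inferiority is declared.
- The mean loss is 50/48 = 1.04. With SD 2.05, the one-sided 90% t-limit is -1.04 - 1.30 × 2.05/√48 = -1.43, well beyond -0.64.

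**5. Error rate if 0.64 is a mean.** With normal differences rounded to whole lesions (SD 2.09, 48 pairs, true mean loss 0.64), the signed-rank test declares non-inferiority in about 17% of trials and the t-limit in about 10%; nominal is 10%. When a fraction of patients each lose the same number of lesions and the rest tie, the signed-rank rate depends on the pattern: 6% if 32% of patients lose 2, and 55% if 21.3% lose 3. The t-limit gives 11% and 17% in those two patterns.

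**The case against.** Much of the case against stands and limits the point.

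- **Pairs.** A signed-rank test can use only pairs, and 14.2.1 says so. Section 8.1 can be read as putting cohort 1 into the comparison, which leaves room for 8 unpaired patients. Central review of all imaging presupposes that scans are obtained, and the 6-month wording in 11.1 is neutral on direction apart from its tense. Sections 12.1.1 and 13.2 read as if the comparator scan were required. A reader might infer that the comparison will be underpowered. The documents do not show that; they show only that nothing secures the pairs.
- **Margin.** It would be too much to say that 0.64 has no unit at all. The variable is the number of lesions, so lesions per patient is the natural reading. On a ratio or log scale, the result for margins between 0.5 and 1 would not apply in this form.
- **Type I error.** A reader might infer that the test is invalid. For its own parameter, the pseudomedian, there is no inflation. The excess over 10% arises only if the margin is meant as a mean, and the largest rates come from all-or-nothing patterns that the plan does not assume.
- **Model.** At SD 2.09 the signed-rank test on rounded differences has about 86% power at 48 pairs, above the formula's 80%. Recalibrated to 80% (SD about 2.35), it loses power with fewer pairs much as in the table.
- **Standing.** The endpoint is secondary, in a Phase 1 study. The McNemar comparison in 14.2 could show large losses, but it has no non-inferiority margin and does not settle this conclusion.

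**Conclusion.** The concern holds in this form: the plan does not secure the 48 pairs on which its 80% rests, and its passages on whether the comparator scan is required must be reconciled. How many pairs will be missing is unknown. The loss would be 3 points at 44 pairs and about 21 at 24 if the 80% is for one bound, and 4 and 40 points if it is for two. These figures rest on paired SDs back-solved from the plan's own 80%, not on data. The 80% should be called unverifiable, not wrong.

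On the margin, the missing items are the parameter and the number of bounds. Read as lesions per patient, the test cannot distinguish 0.64 from any other margin between 0.5 and 1, and it can declare non-inferiority at an observed mean loss above 0.64. That is a fault only if the margin is meant to limit the mean. This should be fixed before the comparison is analysed.

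**What to change.** 1. In 14.2.1 and 10.2, define evaluable for the lesion comparison as having both scans, and say whether cohort 1 counts. In 11.1, apply the 6-month window and the retrieval step also to Ga scans done after the 18F scan. Reconcile 6.2, 7.2.2 and 9.1 with 12.1.1 and 13.2.
2. Either restate the power for the number of pairs expected, or count replacements in pairs until 48 are reached.
3. Say whether one bound (non-inferiority) or two (equivalence) are tested, and give the power for that choice with the within-patient discordance assumption, checked by simulation on whole-number counts.
4. State the parameter of 0.64. If it is the mean, base the conclusion on a one-sided 90% paired limit for the mean difference (both bounds for equivalence), with the signed-rank test as supportive. If it is the pseudomedian, keep the test and state that the margin does not limit the mean loss.

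**Cost.** Section 17.4 requires a formal amendment for any change that is not administrative, and restating power or margin is not plainly administrative. The text affected is 14.2.1, 10.2, 11.1 and 13.2, plus the synopsis, 7.2.2 and 9.1 if unpaired patients are limited. The stated power may fall: with rounded differences, SD 2.09, 48 pairs and one bound, the t-limit has 79% against about 86% for the signed-rank test. The t-limit is also more sensitive to outlying patients, and its error rate can reach 17% in skewed patterns.

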14.2.3 Somatostatin receptor expression

SUV measures from $[^{18}\text{F}]\text{-FET-}\beta\text{AG-TOCA}$ will be summarized by lesion. The correlation of SUV measures to ordinal measures of SSTR1-5 detected by IHC staining of the diagnostic biopsy (-, +, ++, +++) will be evaluated using non-parametric Kruskal-Wallis tests.

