7.2.3 Translational end-points

1. Assess expression of SSTR1-5 in biopsy specimens and compare with PET parameters
2. Evaluation of possible adverse effects

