11.2 PET Procedure (Day 0)

The tracer is made at GMP standards, at Imanova Limited which are GMP certified

- PET/CT scans will be carried out in the Imanova Limited, at the Hammersmith hospital site, [name]
- Transportation will be arranged as required for patients
- Between 30 min to 2 min before dosing the different parameters will be assessed as reported in Table 2 (Cohort 1). Between 180 min to 5 min before dosing the different parameters will be assessed as reported in Table 3 (Cohort 2).
- For patients in cohort 1 two Intravenous cannulae will be placed in the arm in order to inject the tracer, [¹⁸F]-FET-βAG-TOCA and for metabolites (approximately 200ml of blood samples will be taken from this line). For patients in cohort 2 one Intravenous needle will be placed in the arm in order to inject the tracer, [¹⁸F]-FET-βAG-TOCA.
- Patient will be asked to lie flat on the PET-CT scanner bed
- The bed will move into the scanner which looks like a short tunnel
- Patients in cohort 1 will have ECG monitoring. Vitals will be assessed (pre-specified time points, as reported in Table 2).
- A non contrast enhanced CT will be performed to define the region of interest. [¹⁸F]-FET-βAG-TOCA will be injected intravenously. PET/CT scanning will be then subsequently performed. In cohort 1 patients will undergo 5-6 whole body sweeps (vertex to mid thighs) lasting approximately 3-4 hours with a gap in between. Patients in cohort 2 will have a PET/CT scan which will last up to 70 minutes
- Patients in cohort 1 will be admitted for overnight stay.
- Tumour biopsies at diagnosis will be retrieved for analysis of SSTR1-5 expression after Day 0 on successful completion of subject scan.

11.3 Radiation dosimetry.

Table 4. Radiation dosimetry description for [¹⁸F]-FET-βAG-TOCA PET and CT.

| Tracer | [¹⁸ F]-FET-βAG-TOCA | CT |
|-------------------------------------|--------------------------------------|--------------------------------|
| Maximum dose per scan(MBq) | 165 | |
| Conversion factor (mSv/MBq) | 0.04 | |
| Effective dose per scan (mSv) | 5.11 | 2.4 |
| No of scans | 1 | 2 (cohort 1) 1 (cohort 2) |
| Total effective dose (mSv)/ patient | 5.11 mSv cohort 1 12 mSv cohort 2 | 4.8 (cohort 1), 2.4 (cohort 2) |

Therefore total effective dose per patient is 12mSv for cohort 1 and 14mSv for cohort 2 (max dose injected 370Mbq).

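### An unordered Kruskal-Wallis test is named for a correlation between SUV and ordered receptor grades, and the unit of that test (patient or lesion) is not stated

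*Combined protocol and SAP*

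**What the plan says.** Section 14.2.3 (cohort 2) says that SUV measures "will be summarized by lesion". The next sentence gives the aim, "The correlation of SUV measures to ordinal measures of SSTR1-5", and describes the receptor data as "ordinal measures of SSTR1-5 detected by IHC staining of the diagnostic biopsy", scored -, +, ++ or +++. The relation "will be evaluated using non-parametric Kruskal-Wallis tests". Section 14.1.4 uses the same wording for cohort 1.

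On tissue, section 8.1 says that each patient's "original diagnostic tumour biopsy (paraffin fixed) will be obtained". Section 11.2 uses the plural: "Tumour biopsies at diagnosis will be retrieved for analysis of SSTR1-5 expression". No section describes matching a biopsy to a particular lesion on the scan.

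Section 7.2.3 lists the analysis as a translational end-point: "Assess expression of SSTR1-5 in biopsy specimens and compare with PET parameters". Section 7.1.2 does the same for cohort 1. The plan gives no sample size, power, significance level or effect size for it.

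**The concern.** There are two separate problems.

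**The test does not fit the question.** The plan calls the grades ordinal and asks for a correlation. Kruskal-Wallis asks only whether SUV differs somewhere among the four groups. Relabelling the grades in any order leaves its result unchanged, so a significant result could arise with + above +++. It also gives no estimate of how strongly uptake follows expression. If uptake does rise with expression, the test is more likely to miss it than one that uses the order.

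**The unit is undefined.** SUV is described per lesion, while the grade belongs to a patient's diagnostic specimen. If every lesion enters the test, one patient's grade is copied across all of that patient's lesions and the lesions count as independent observations. If one value per patient enters, the plan does not say which value. The choice is left open until the data have been seen.

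At stake is whether the study can say that uptake follows receptor expression, which is the biological rationale for the tracer in section 5.2.

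**Working it through.** The plan has no figure of its own for this analysis, so there is nothing to reproduce. The check is by simulation.

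**Inputs from the plan.** Four ordered grades (14.2.3). 48 patients, borrowed from the paired-imaging power statement in 14.2.1. Lesions per patient from the planning distribution in 14.2.1, a truncated log-normal with "median = 5, range = 1 to 25".

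**Assumed, because the plan is silent.** Two-sided level 0.05. SUV rising linearly with grade by 0.3 or 0.4 SD per step. Grades either equally frequent or skewed high (10/15/30/45%). Log-SD of the lesion count 0.8, with 0.5 and 1.0 also tried. Within-patient correlation of SUV (ICC) from 0 to 0.7.

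**Step 1: power with one value per patient, N = 48.** Model: SUV = slope × grade + standard normal error, grade = 0, 1, 2, 3; 4,000 datasets per setting.

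| Grades | Slope (SD per grade) | Kruskal-Wallis | Kendall/Jonckheere-type | Spearman |
|---|---|---|---|---|
| equal | 0.3 | 39.0% | 58.4% | 59.0% |
| equal | 0.4 | 63.9% | 81.8% | 82.4% |
| skewed high | 0.3 | 29.3% | 46.1% | 46.5% |
| skewed high | 0.4 | 52.6% | 70.1% | 70.4% |

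The gaps to Spearman are 59.0 − 39.0 = 20.0, 82.4 − 63.9 = 18.5, 46.5 − 29.3 = 17.2 and 70.4 − 52.6 = 17.8 points. Repeat simulations with equal grades gave 38% to 41% against 58% to 61% at 0.3 SD, and 63% to 66% against 82% to 84% at 0.4 SD.

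The reason is that Kruskal-Wallis spreads the signal over 3 degrees of freedom (critical value 7.81), while a trend test puts it on 1 (critical value 3.84).

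**Step 2: false positives if lesions are pooled.** Each patient has one grade, unrelated to SUV. Lesion SUVs share a patient effect with the stated ICC. The simulated mean is 6.364 lesions per patient, so 48 × 6.364 ≈ 305 lesions; 3,000 datasets per setting, equal grades.

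| ICC | Lesion-level Kruskal-Wallis | Kruskal-Wallis on patient means | Spearman on patient means |
|---|---|---|---|
| 0 | 4.5% | 3.7% | 5.2% |
| 0.1 | 23.3% | 5.1% | 5.6% |
| 0.3 | 50.9% | 5.0% | 5.7% |
| 0.5 | 67.7% | 4.8% | 4.5% |
| 0.7 | 77.3% | 4.2% | 4.7% |

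At ICC 0.3 the lesion-level rate is 41.0% with log-SD 0.5 and 55.3% with log-SD 1.0.

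**Step 3: check by hand.** With unequal lesion counts m, the design effect is about D = 1 + ICC × (E(m²)/E(m) − 1), and here E(m²)/E(m) = 9.755. The pooled statistic then behaves roughly like D times a chi-square on 3 degrees of freedom, so the false-positive rate is about P(χ²₃ > 7.815/D).

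- ICC 0.1: D = 1 + 0.1 × 8.755 = 1.875; P(χ²₃ > 4.167) ≈ 24%.
- ICC 0.3: D = 3.626; P(χ²₃ > 2.155) ≈ 54%.
- ICC 0.5: D = 5.377; P(χ²₃ > 1.453) ≈ 69%.
- ICC 0.7: D = 7.128; P(χ²₃ > 1.096) ≈ 78%.

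These agree with the simulation to within about 3 points.

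**The case against.** **The plan does not say that lesions enter the test.** A reader might infer that it does, and that the analysis is therefore bound to give false positives. The text does not support that. The per-lesion wording governs the summary of SUV, and the sentence naming the test gives no unit. The same words would fit testing the biopsied lesion or a patient summary. One biopsy per patient is also not a stated rule: sections 8.1 and 14.2.3 use the singular, while 7.1.2, 7.2.3 and 11.2 use plurals, which may only reflect many patients. This objection stands, so the inflation is conditional on pooling.

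**The two harms do not add up.** A reader might conclude that the analysis both loses power and over-rejects. The power loss was shown for a patient-level analysis and the inflation for a lesion-level one. No single reading was shown to produce both.

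**Kruskal-Wallis is a valid test.** With one value per patient at N = 48 its error rate is close to 5%, and it keeps power against a non-monotone pattern. That is true, but the plan asks for a correlation with ordinal grades, which is a question about a monotone relation.

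**The inputs are assumed.** Equal grades may be unrealistic, since section 5 says that 70 to 90% of these tumours express subtypes 2 and 5; skewed grades lower the power of both tests. Inclusion criterion 3 admits some patients without histology, so fewer than 48 may have tissue. These points change the level of power but do not make the test fit the question.

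**A new test does not rescue cohort 1.** With 12 patients the chi-square version of Kruskal-Wallis rejects only about 2% of the time under the null, which exaggerates any comparison at that size. Even Spearman reaches only about 25% power at 0.4 SD per grade with equal grades. No cohort 1 comparison is relied on here.

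**Conclusion.** The mismatch between test and aim holds on the plain text of 14.1.4 and 14.2.3. For a monotone relation of 0.3 to 0.4 SD per grade with one value per patient and N = 48, it costs about 17 to 20 points of power: about 40% against 60% and 65% against 83% with equal grades, and about 52% against 70% at 0.4 SD with grades skewed high.

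The missing unit of analysis also holds, as an omission. Its consequence is conditional: a false-positive rate of about 23% to 77% at a nominal 5% if lesions are pooled as independent and the within-patient correlation is 0.1 to 0.7, and no inflation if one value per patient is used.

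The slopes, grade mix, significance level, spread of lesion counts and within-patient correlations are all assumptions. The weight is moderate, because this is a translational endpoint and no primary or secondary conclusion rests on it.

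**What to change.** In 14.1.4 and 14.2.3:

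- State that the patient is the unit, with one SUV per patient: the biopsied lesion if it can be identified, otherwise the patient's median.
- Replace Kruskal-Wallis with Spearman's correlation or the Jonckheere-Terpstra test, and report the coefficient with a 95% interval.
- If all lesions are to be used, fit a model with a patient random effect and grade as an ordered score.

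The cost is wording only, with no extra data or patients. The one statistical downside is less power against a non-monotone pattern.
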